5.8.2. Analysis of 7-point SMBG profile

The 7-point SMBG profiles consist of pre-meal and 2-hour postprandial SMBG measurements for the morning, midday, and evening meals, and one measurement at bedtime. Patients will be asked to perform two 7-point SMBG profiles over a 24-hour period on 2 nonconsecutive days, in the 2-week period prior to prespecified office visits (Visits 3 [Week 0], 12 [Week 12], 17 [Week 28], and early termination [ET]). In general, the mean of the two daily values will be used for reporting purpose. If 7-point SMBG is not performed, then data from the most recent nonconsecutive 4-point SMBG (3 before each meal and one at bedtime) profiles can be used. If more than 2 SMBG profiles are available, the 2 most recent profiles on nonconsecutive days should be used.

The following variables for 7-point SMBG profile will be analyzed using MMRM model:

1. Pre morning meal BG (mg/dL)
2. 2-hour postprandial measurement for morning meal BG (mg/dL)
3. Pre midday meal BG (mg/dL)
4. 2-hour postprandial measurement for midday meal BG (mg/dL)
5. Pre evening meal BG (mg/dL)
6. 2-hour postprandial measurement for evening meals BG (mg/dL)
7. Bedtime BG (mg/dL)
8. Mean of all pre-meal BG (mg/dL)
9. Mean of all postprandial BG (mg/dL)
10. Mean of all meals 2-hour excursion (mg/dL)
11. Mean of all 7-point BG (mg/dL)

For before and 2 hours after meal BG and bedtime BG (Reports 1-7), the mean BG value at each visit is calculated as the average of 2 daily BG values. The change from baseline is calculated as the mean BG value at Week 12 and Week 28 minus the mean BG value at the baseline.

For mean of all pre-meal BG (Report 8), the pre-meal daily mean is calculated as the average BG values collected for before morning, midday and evening meals on a particular day. The mean of all pre-meal BG at each visit is calculated as the average of 2 pre-meal daily means. The change from baseline is calculated as the mean of all pre-meal BG at Week 12 and Week 28 minus the mean of all pre-meal BG at baseline.

For mean of all postprandial BG (Report 9), the post-meal daily mean is calculated as the average of 2-hour postprandial BG values of morning, midday and evening meals on a particular day. The mean of all postprandial meals BG at each visit is calculated as the average of 2 post-

meal daily means. The change from baseline is calculated as the mean of all postprandial BG at Week 12 and Week 28 minus the mean of all postprandial BG at baseline.

For mean of all meals 2-hour excursion at each visit (Report 10), the daily mean for all meals is calculated as the average of glucose excursion for morning, midday and evening meals on a particular day. The mean of all meals 2-hour excursion at each visit is calculated as the average of 2 daily means. The change from baseline is calculated as the mean of all meals 2-hour excursion at Week 12 and Week 28 minus the mean of all meals 2-hour excursion at baseline.

For mean of all 7-point BG (Report 11), the daily mean is calculated as the average of 7 BG values collected on a particular day. The mean of all 7-point BG at each visit is calculated as the average of 2 daily means. The change from baseline is calculated as the mean of all 7-point BG at Week 12 and Week 28 minus the mean of all 7-point BG at baseline.

Actual and change from baseline of 7-point SMBG will be summarized using ITT population, and analyzed using MMRM with treatment, OAM usage, visit, baseline HbA1c strata (<8.5%, and $\geq 8.5\%$) and treatment-by-visit interaction as fixed effects, baseline 7-point SMBG as covariate and patient as a random effect. An unstructured covariance structure will be used to model the within-patient variability and implicitly adjusts for missing data. If this analysis fails to converge, then other covariance structures will be tested in the order mentioned in Section 5.2.

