- g. Preexisting conditions and adverse events will be reviewed during telephone contacts but recorded on the eCRF at subsequent office visits.
- h. Concomitant medications will be reviewed during telephone contacts but recorded on the eCRF at subsequent office visits.
- i. Hypoglycemic events will be reviewed during telephone contacts but recorded on the eCRF at subsequent office visits.
- j. Patient training should occur at Visit 2. Additional training can also be performed at Visit 3, when needed. Patient training will include training on TTT insulin dose adjustment algorithm.
- k. Retraining and review of device training to be performed as needed.
- l. Dispense only as needed.
- m. Safety data to be captured after discontinuation of study drug during safety follow-up period.
- n. Patients will be asked to perform two 7-point SMBG profiles on two nonconsecutive days, in the 2-week period prior to Visit 3, as well as prior to Visit 12 and Visit 17. A 7-point SMBG consists of measurements before and 2 hours after each of 3 main meals within the same day and at bedtime. If 7-point SMBG is not performed, then data from the most recent nonconsecutive 4-point SMBG (3 before each meal and one at bedtime) profiles can be used. If more than 2 SMBG profiles are available, the 2 most recent profiles on nonconsecutive days should be used. In the weeks that the 7-point profiles are performed, the 4-point SMBG profiles will not be needed.
- o. Review/record 7-point SMBG profile(s), only if applicable, based on previous study visit.
- p. Patients will be encouraged to collect a daily fasting BG and a weekly 4-point SMBG. Missing a fasting BG measurement will not be considered a protocol deviation.

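### Does SAP 5.8.2 need a further rule for substituted 4-point glucose profiles and for visits with only one usable 7-point day?

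*SAP*

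**What the plan says.** SAP 5.8.2 collects two 7-point profiles on nonconsecutive days in the two weeks before Visits 3, 12 and 17, and also for early termination. It gives a fallback: "If 7-point SMBG is not performed, then data from the most recent nonconsecutive 4-point SMBG" profiles, made up of three pre-meal values and a bedtime value, can be used. When there is a surplus, "If more than 2 SMBG profiles are available, the 2 most recent profiles on nonconsecutive days should be used". Footnote n of the protocol's Schedule of Activities gives the same two rules.

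The reporting rule is worded with some latitude: "In general, the mean of the two daily values will be used for reporting purpose". For Reports 1 to 7, "the mean BG value at each visit is calculated as the average of 2 daily BG values". For Report 11, the all-points mean, "the daily mean is calculated as the average of 7 BG values collected on a particular day", and then "The mean of all 7-point BG at each visit is calculated as the average of 2 daily means". Reports 8 to 10 follow the same two-day pattern.

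The change from baseline goes into an MMRM. SAP 5.2 adds a rule for every variable: a missing baseline is replaced by the latest available value before Visit 3. SAP Table 4.1 places glucose-profile change among the additional secondary endpoints, outside the set controlled for type I error.

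**The concern.** Two things look unfinished. First, the permission to use 4-point data is not tied to particular reports. A 4-point day has no post-meal values, so its plain average lies below that of a 7-point day in the same patient. If a programmer put a four-value mean into Report 11, profile type would shift the result.

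Second, visit values are averages of two days, and the text covers more than two profiles but not fewer. With one 7-point day, alone or beside a 4-point day, Report 11 could be set to missing, taken from the single day, or averaged with a four-value mean. Two programmers could differ. At stake are the reproducibility of an additional secondary endpoint, some precision and, under the third option, a possible bias between arms.

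**Working it through.** The documents give no figure to reproduce here, so the check compares what each report needs with what a 4-point day contains, and then sizes the alternatives under stated assumptions.

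**Step 1. Which reports can a 4-point day feed?** It contains three pre-meal values and one bedtime value (SAP 5.8.2).

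| Report | Needs | Supplied by a 4-point day |
|---|---|---|
| 1, 3, 5 | one pre-meal value each | yes |
| 7 | bedtime value | yes |
| 8 | three pre-meal values | 3 of 3 |
| 2, 4, 6 | one post-meal value each | no |
| 9 | three post-meal values | 0 of 3 |
| 10 | pre- and post-meal values for three meals | 3 of 6, so no excursion can be formed |
| 11 | seven values | 4 of 7 |

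Ten of the eleven reports are settled by content alone. Report 11 is settled by its definition, because four values do not make an average of seven.

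**Step 2. What if a four-value mean were entered in Report 11 anyway?** Let P be the pre-meal level, P + E the 2-hour post-meal level and P + B the bedtime level, with B between 0 and E.

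- 7-point mean = P + (3E + B)/7
- 4-point mean = P + B/4
- Gap G = (3/7)(E − B/4)

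The documents give neither E nor B. Assuming E of 30 to 60 mg/dL:

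- E = 30, B = 30: G = (3/7)(22.5) = 9.6 mg/dL
- E = 60, B = 0: G = (3/7)(60) = 25.7 mg/dL

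If one of the two days is a 4-point day, the visit value falls by half of this, 4.8 to 12.9 mg/dL. With equal use and equal E in both arms, the between-arm difference is unchanged. With 10% use in each arm, both days 4-point, and E of 30 on dulaglutide against 50 on placebo, the contrast (dulaglutide minus placebo) moves by 0.1 × (21.43 − 12.86) = +0.86 mg/dL at B = 0, or 0.1 × (16.07 − 9.64) = +0.64 at B = E. These shifts need a departure from the Report 11 definition. They do not describe the plan as written.

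**Step 3. One complete 7-point day.** Two readings respect the definitions: use the day, or treat the visit as missing. Using it keeps every such patient, with a noisier value. For the missing reading, let q be the share of patients with one complete day at a given visit (assumed; no rate is given), with 123 completers per arm (SAP 5.1).

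- Independent loss at baseline and Week 28: share kept (1 − q)², simple standard-error ratio 1/(1 − q).
- Loss at Week 28 only, if the SAP 5.2 baseline rule admits the single day: share kept 1 − q, ratio 1/√(1 − q).

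| q | Kept, both visits strict | SE ratio | Kept, baseline rescued | SE ratio |
|---|---|---|---|---|
| 5% | 0.9025 × 123 = 111 | 1.05 | 0.95 × 123 = 117 | 1.03 |
| 10% | 0.81 × 123 = 100 | 1.11 | 0.90 × 123 = 111 | 1.05 |
| 20% | 0.64 × 123 = 79 | 1.25 | 0.80 × 123 = 98 | 1.12 |

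The ratios treat the analysis as complete-case at Week 28. The MMRM also uses Week 12, so they overstate the cost of a missing Week 28 value. If the same patients miss days at both visits, the share kept moves from the strict column towards 1 − q.

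**The case for a change.** The best case for a change is that the MMRM works on visit values and cannot decide whether a one-day visit has one. Nor does a mixed pair require poor compliance. Footnote p of the Schedule of Activities says "Patients will be encouraged to collect a daily fasting BG and a weekly 4-point SMBG", but Protocol 7.2.2.2 makes the 4-point profile a requirement at least once a week. A patient who completes both 7-point profiles in the first week of the window and a 4-point profile in the second has three profiles, and the surplus rule read alone would select the 4-point day. Excursions could also differ by arm, since Protocol 3.2 lists delayed gastric emptying and glucose-dependent insulin secretion among dulaglutide's effects, so mixing profile types might not cancel between arms.

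Part of this stands: no sentence covers a single day after baseline, and the order of preference between profile types is implied, not stated. But the fallback applies only when the 7-point profile was not done, so taking 7-point days first is the natural reading. Where a 4-point day is selected all the same, it still has no value for Report 11, and the question returns to the one-day case. The arm-dependent bias therefore needs a step that the SAP's definition rules out.

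**Conclusion.** No change to the plan is needed. The mapping of 4-point data to reports follows from the content of the profile and the definition of Report 11. The remaining gap, use or omit a lone day, is a derivation detail that analysts fill sensibly. The SAP's own wording treats the two-day mean as the general rule and leaves room for a one-day convention. Using the day costs some noise. Omitting it costs precision, with a standard error at most about 1.03 to 1.25 times as large for q of 5% to 20%.

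Those figures rest on an assumed q, on 123 completers per arm and on a complete-case approximation that overstates the loss. The conclusion also assumes that the programmer follows the seven-value definition. A written convention would record the choice without changing what the endpoint measures, and no primary or key secondary result depends on it.

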5.8.3. Analysis of Insulin Glargine Dose

Actual and change of daily insulin glargine dose from baseline measurements will be summarized using ITT population. Change from baseline of glargine dose will be analyzed using MMRM model and will include treatment, OAM usage, visit, baseline HbA1c strata (<8.5%, and $\geq 8.5\%$), treatment-by-visit interaction as fixed effects, and baseline glargine dose as a covariate. Daily insulin dose of each visit is defined as the dose of the last dose before each visit.

5.9. Tertiary/Exploratory Efficacy Analyses

5.9.1. Insulin Glargine Treat-to-Target (TTT) Algorithm Assessment

The number of insulin dose assessments per the TTT algorithm, and compliance with the TTT algorithm at Week 6, 8 and 12 (number of assessments performed correctly; number of assessments that required dose change; number of assessments for which the outcomes were correctly followed by the patient) and frequency of insulin dose adjustments will be analyzed using an ANCOVA model including treatment, OAM usage, and baseline HbA1c strata. Reasons for patients not following the outcome of the assessment will be analyzed using Fisher's exact test.

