5.4. Scientific Rationale for Study Design

Combination therapy of basal insulin and GLP-1 receptor agonist is broadly used and previous studies have demonstrated the efficacy and safety of this combination. In the AWARD-9 clinical trial (Study H9X-MC-GBDI), a significantly greater proportion of patients treated with dulaglutide added to basal insulin with or without metformin (66.7%) achieved HbA1c <7.0% compared to the addition of placebo with further titration of insulin glargine (33.3%). The better glycemic control with the addition of dulaglutide was achieved without increasing the risk of hypoglycemia and with weight benefit (Pozzilli et al. 2017).

This study (H9X-MC-GBGO) is designed to compare the benefits and risks of dulaglutide 1.5 mg QW as add-on to titrated insulin glargine with placebo QW as add-on to titrated insulin glargine, with metformin and/or acarbose, in Chinese patients with T2D. The trial design will enable assessment of the effects of these interventions on daily and long-term glycemic control, as well as on safety variables.

Patients selected to participate in this study will be those who require intensification of their current basal insulin regimen due to inadequate glycemic control, as indicated by HbA1c value above the ADA/EASD established target of 7.0%.

To ensure that patients randomized to receive placebo also have the opportunity for effective treatment (ie, basal insulin optimization) during the treatment period, only patients who require insulin glargine dose up-titration will be randomized to continue in the treatment period of this study.

To ensure a valid comparison of the randomized study treatments, it is important that insulin glargine is titrated in an optimal way throughout the entire study. Patients will be required to use a TTT algorithm, which has been shown to be effective in enabling a high proportion of patients

with T2D to achieve their therapeutic targets when treated with insulin glargine (Davies et al. 2005).

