9.1.3. Exploratory Efficacy Measures

The following exploratory efficacy measures will be evaluated:

- frequency of insulin dose adjustments at 28 weeks;
- number of insulin dose assessments per TTT algorithm and compliance with the TTT algorithm at 6, 8, and 12 weeks.

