10.3.3.3. Tertiary/Exploratory Analyses

The number of insulin dose assessments per the TTT algorithm, compliance with the TTT algorithm (number of assessments performed correctly, number of assessments that required dose change, number of assessments for which the outcomes were correctly followed by the patient, and reason the outcomes of assessments were not followed by the patient) and frequency of insulin dose adjustments will be analyzed using an ANOVA model, including treatment, OAM usage (metformin alone, acarbose alone, metformin and acarbose), and baseline HbA1c stratum.

The other objectives include triple endpoint (HbA1c <7% and no weight gain [<0.1 kg] at 28 weeks, and no documented symptomatic hypoglycemia [BG <3.9 mmol/L] during the maintenance period); double endpoint (HbA1c <7% at 28 weeks and no documented symptomatic hypoglycemia [BG <3.9 mmol/L] during the maintenance period); Proportion of patients achieving HbA1c target <7.0% and without weight gain (<0.1 kg) at 28 weeks.

Furthermore, we will conduct some additional efficacy analysis without censoring the data after rescue therapy or premature treatment discontinuation (whichever occurs first). Missing endpoints will be imputed by jumping to the reference method. Measurements include actual HbA1c, body weight and FSG and frequency counts and percentage of patients achieving the HbA1c target of <7.0% and changes in these measures from baseline. We will analyze HbA1c, body weight and FSG by ANCOVA. Percentages of patients achieving the target of HbA1c <7.0% will be analyzed using longitudinal logistic regression with repeated measurements.

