5.1. Determination of Sample Size

A total of approximately 290 patients (145 per group) will be randomized to have approximately 246 completers (123 per group) to show dulaglutide add-on titrated insulin glargine is superior to placebo add-on titrated insulin glargine with 90% power assuming a treatment difference of 0.5% in HbA1c reduction, standard deviation (SD)=1.2%, and dropout rate of 15%, and 2-sided alpha of 0.05. The screen failure rate is estimated as 40%. Approximately 483 patients will be screened.

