5.2. General Considerations

This plan describes all priori statistical analyses for efficacy and safety that will be performed.

Statistical analysis of this study will be the responsibility of Eli Lilly and Company (Lilly), although implementation of the statistical analysis may be delegated to a third party. Any change to the data analysis methods described in the protocol will require an amendment ONLY if it changes a principal feature of the protocol. Any other change to the data analysis methods described in the protocol, and the justification for making the change, will be described in this SAP and/or in the clinical study report (CSR). Additional exploratory analyses of the data will be conducted, as deemed appropriate.

All analyses will be implemented using Version 9.4 SAS or higher.

Unless otherwise specified, listings will include all randomized patients. Both efficacy and safety analyses will be conducted using the intent-to-treat (ITT) population. Unless otherwise specified, efficacy data from patients who started rescue therapy or premature treatment discontinuation (whichever occurs first) will be censored from the point of initiating rescue treatments or early discontinuation onwards. Safety analysis will not censor this part of data. Selected analyses will also be conducted using the per-protocol (PP) and Completers populations. The PP and Completers populations are subsets of the ITT population.

Unless otherwise noted, all tests of treatment effects will be conducted at a 2-sided alpha level of 0.05, and confidence intervals (CIs) will be calculated at 95%, 2-sided. All tests of interactions between treatment groups and other factors will be conducted at a 2-sided alpha level of 0.10.

The baseline data will be collected at Visit 3. For all variables, including HbA1c, if baseline data are missing, the last non-missing measurement taken prior to this visit will be used for the baseline measurement.

Patients will be randomized in a 1:1 ratio to (1) dulaglutide 1.5 mg QW add-on to insulin glargine or (2) placebo QW add-on to insulin glargine, with metformin and/or acarbose. Patients will also be stratified by HbA1c at Visit 1 (screening) (<8.5% vs. \geq 8.5%) and OAM usage (metformin alone, acarbose alone, metformin and acarbose) at Visit 3 (randomization) to achieve

between-group comparability and to mitigate against confounding the effects of the treatments with severity of disease or treatment with metformin and/or acarbose.

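### SAP 5.9.1 compares treat-to-target compliance as raw counts with no denominator, and one of the counts reflects need for a dose change rather than compliance

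*SAP*

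**What the plan says.** SAP 5.9.1 covers the number of insulin dose assessments and compliance at Weeks 6, 8 and 12. Compliance is spelled out as three counts: assessments performed correctly, then "number of assessments that required dose change; number of assessments for which the outcomes were correctly followed by the patient". These counts and the frequency of dose adjustments go into an ANCOVA with treatment, OAM usage and baseline HbA1c strata. Reasons for not following an outcome are compared by Fisher's exact test.

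Protocol 10.3.3.3 lists the same counts, including "number of assessments for which the outcomes were correctly followed by the patient", under an ANOVA with the same terms. Protocol 9.1.3 names the measure as "compliance with the TTT algorithm at 6, 8, and 12 weeks". Neither document gives a ratio, an offset, or the base over which following is counted.

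Four other places bear on this:
- Protocol 7.2.2.2.1 makes a required change depend on fasting glucose and recorded hypoglycaemia.
- Protocol 7.2.2.2 sets assessments at once weekly after Week 4.
- A footnote to the Schedule of Activities has algorithm compliance entered at Visits 8, 10 and 12 for the period since the previous visit.
- Protocol 5.4 says that for a valid comparison "it is important that insulin glargine is titrated in an optimal way throughout the entire study".

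**The concern.** The question is whether the two arms follow the algorithm equally well. The null hypothesis tested is that the mean counts are equal. The two coincide only if the arms have equal numbers of occasions to comply.

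The count of required changes has no compliance content. It records how often fasting glucose or hypoglycaemia called for a new dose, and Protocol 3.1 reports that adding a GLP-1 receptor agonist improved glycaemic control and reduced insulin dose. A significant difference could therefore be drug effect reported under a compliance label.

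The count of outcomes followed is ambiguous. If it covers only required changes, it is need multiplied by following, and the two cannot be separated. If it covers every assessment, including those whose outcome is to leave the dose alone, it is distorted only when that outcome is followed more often than a required change.

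At stake is how the exploratory titration result can be read. A difference need not mean unequal compliance, and under the required-changes reading no difference need not mean equal compliance.

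**Working it through.** **1. The plan's own figure.** No design figure is given for algorithm compliance. The only one is the primary sample size, "with 90% power assuming a treatment difference of 0.5% in HbA1c reduction", with SD 1.2%, 15% dropout and "2-sided alpha of 0.05". Per arm: n = 2 × (1.960 + 1.282)² × 1.2² / 0.5² = 2 × 10.51 × 5.76 = 121.1, so 122 (244 in all, against 246 stated). Power at 123 per arm is 0.904. Then 246 / 0.85 = 289.4, so 290 randomised, and 290 / 0.60 = 483 screened. The stated figures reproduce, so 145 and 123 per arm are used below.

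**2. Assessments per window.** Weekly assessments between office visits at Weeks 4, 6, 8 and 12 give about 2, 2 and 4, or 8 in total. If telephone visits count as the previous visit, the numbers are 1, 1 and 2.

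**3. Assumptions, none in the documents.** An assessment requires a change with probability 0.7 on placebo and 0.7 down to 0.4 on dulaglutide. A required change is followed with probability 0.8 when compliance is equal, and about 0.6 to 0.69 on placebo when it is not. Patients vary (beta distribution, a + b = 10), and need and following are independent.

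**4. Expected counts, two assessments, equal following, need 0.7 against 0.5.**
- Required: 2 × 0.7 = 1.40 against 2 × 0.5 = 1.00.
- Followed, required changes only: 1.40 × 0.8 = 1.12 against 1.00 × 0.8 = 0.80.
- Followed, all assessments, same 0.8 throughout: 1.60 in both arms.
- Followed, all assessments, no-change outcomes always followed: 2 × (0.56 + 0.30) = 1.72 against 2 × (0.40 + 0.50) = 1.80.

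Hand check on the first line, with plain binomial variance: SE = √[(2 × 0.7 × 0.3 + 2 × 0.5 × 0.5) / 145] = √(0.92 / 145) = 0.080, so 0.40 / 0.080 = 5.0 standard errors. Between-patient variation lowers this slightly.

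**5. Simulated rejection rates under equal following.** Model of SAP 5.9.1, 145 per arm, 1,000 runs per setting, for 2 / 4 / 8 assessments:

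| Measure | Need 0.7 v 0.5 | Need 0.7 v 0.6 |
|---|---|---|
| Required a change | >0.99 in all | 0.67 / 0.90 / 0.97 |
| Followed, required changes only | 0.96 / 1.00 / 1.00 | 0.46 / 0.73 / 0.86 |

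In addition:
- With all assessments as the base, rejection is about 0.05 when both kinds of outcome are followed equally. At need 0.7 against 0.5 it is 0.29 / 0.48 / 0.69 when no-change outcomes are nearly always followed.
- Performed correctly stays at about 0.05.
- The proportion followed / required stays at 0.04 to 0.08 across settings.
- With equal need, every measure rejects at about 0.05.

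**6. A real placebo deficit (0.60 followed against 0.80).**
- Need 0.7 against 0.525: the required-changes count cancels exactly, since 0.7 × 0.60 = 0.525 × 0.80 = 0.42. It rejects 0.04 / 0.05 / 0.07. The proportion rejects 0.97 / 1.00 / 1.00, and the all-assessments count about 1.00.
- Need 0.7 against 0.6: the required-changes count has power 0.28 / 0.47 / 0.62.
- Equal need: 0.90 or more.

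Results at 123 per arm are similar.

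**The case against.** The case for leaving the section alone has real weight.

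The text on outcomes followed carries no restriction to required changes, and leaving the dose unchanged is a row of Table GBGO.4, so counting all assessments is the more natural reading. Weekly assessment makes the number due nearly fixed, and the number of assessments and the number requiring a change are reported beside the number followed. Titration is also examined through reasons for not following, glargine dose (SAP 5.8.3), FSG (SAP 5.7.2) and pre-breakfast SMBG (SAP 5.8.2).

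Much of this stands, and it rules out three stronger inferences that a reader might draw:
- **The whole set mainly measures need.** It does not: the number of assessments and the number performed correctly do not depend on need.
- **The plan would miss under-titration of placebo.** That needs the required-changes-only base, which the SAP does not state, together with lower need on dulaglutide that largely offsets the poorer following. The near-zero sensitivity in step 6 sits at an exact cancellation. With all assessments as the base, the same deficit is detected.
- **The primary comparison is undermined.** The measure is exploratory and outside the scheme in SAP 5.3. Protocol 5.4 says how glargine should be titrated; it does not make this test a condition for the HbA1c result.

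Two things do not fall away. The required-change count is not compliance under any reading. The other checks do not isolate compliance either, because dose and glucose can shift with the drug even if every patient follows the algorithm. Nor is the number due quite constant: the windows at Weeks 8 (±4 days) and 12 (±7 days) allow 28 − 11 = 17 to 28 + 11 = 39 days between visits, and Protocol 5.1 lets investigators request more frequent assessments.

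**Conclusion.** The point holds in limited form. SAP 5.9.1 tests counts without a denominator under the name of compliance. One of them, assessments requiring a change, can differ between arms when following is equal. Another, outcomes correctly followed, cannot be interpreted until its base is defined: it moves with need if the base is required changes, and is largely sound if the base is all assessments.

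The size is illustrative. With assumed need of 0.7 against 0.6 and equal following, the required-change count rejects in 67% to 97% of runs; with 0.7 against 0.5, in over 99%; with equal need, in about 5%. The documents give neither need nor follow rates, and Protocol 3.1 supports a direction for need but no figure. The consequence is confined to reading an exploratory result. It still merits a change because the correction is cheap and matches the SAP's own practice: 5.5.5 defines study-drug compliance as a share of scheduled injections, and 5.11.2 models hypoglycaemia rates with a log-days offset.

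**What to change.** In SAP 5.9.1:

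1. State the base for outcomes correctly followed.
2. Analyse compliance as proportions: assessments performed correctly / assessments due, and outcomes followed / all assessments. Add required changes implemented / changes required as a supportive measure. Use a binomial model with patient-clustered robust variance and the existing terms, and report the treatment contrast with a 95% CI.
3. Move the required-change count out of the compliance set and summarise it descriptively.
4. Analyse dose-adjustment frequency as a rate, for example by negative binomial regression with log time on treatment as offset, ending at rescue, study drug stop or Week 28. The SAP does not define frequency, so this also settles its meaning.

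The cost is wording and programming; the protocol already collects the assessment data, doses and dates. If the eCRF count mixes both kinds of outcome, the supportive numerator must be derived from recorded doses.

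The supportive ratio has a real drawback. It conditions on a post-randomisation event and drops patients with no required change. At need 0.7 against 0.5 with two independent assessments, that is 0.3² = 9% on placebo and 0.5² = 25% on dulaglutide. A skipped increase may also create the next required change, which the simulation ignores. It should be read as descriptive or supportive, with the number contributing shown per arm. The all-assessments proportion avoids this selection but keeps the distortion in step 5 if no-change outcomes are followed more readily, so the two should be shown together.
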